8.6 Efficacy Subgroup Analyses

To evaluate the potential impact of demographics and baseline characteristics on efficacy, subgroup analyses may be performed on, but not limited to, the primary efficacy endpoint. For subgroup analyses of binary variables, the difference in the proportions and the corresponding 95% confidence interval (exact unconditional confidence limits) for the difference will also be provided. For subgroup analyses of time-to-event variables, the hazard ratio and the 95% confidence interval based on unstratified Cox proportional hazards model will be provided. For subgroup analyses of continuous variables, the mean difference and the corresponding 95% confidence interval will be provided.

Subgroup analyses will be performed for subgroups including, but not limited to, those defined below:

- Age (18 - < 65 years, ≥ 65 years, ≥ 75 years)
- Race (White, Black or African American, Asian, Other)
- Ethnicity (Hispanic or Latino, Not Hispanic or Latino)
- DIPSS+ Risk Group (Intermediate-1, Intermediate-2, High)
- Baseline Platelet Count ($\leq 200 \times 10^9/L$, $> 200 \times 10^9/L$)
- Type of Myelofibrosis (Primary, Secondary)
- JAK2 V617F Mutation
- CALR Frameshift Mutation

- MPL W515 Mutation
- High Molecular Risk (Yes, No)

High molecular risk (HMR) is defined as any mutation within ASXL1, SRSF2, EZH2, IDH1/2, and U2AF1. For molecular subgroups, analysis for mutation subtypes may also be performed. In addition, correlation among efficacy endpoints, including but not limited to the following, will be explored:

- Anemia response and spleen response
- Depth of spleen response and reduction in grade of bone marrow fibrosis
- Reduction in grade of bone marrow fibrosis and anemia response
- Reduction in variant allele frequency and spleen response.

9.0 Safety Analyses

9.1 General Considerations

Safety data will be summarized for the safety analysis set. Safety summaries will be presented by treatment arm and in total. For the safety analysis, subjects are assigned to a treatment arm based on the treatment actually received, regardless of the treatment randomized. Unless otherwise specified, data after the cutoff date will be excluded from the safety analysis.

9.2 Adverse Events

Adverse events (AEs) will be summarized and presented using primary MedDRA System Organ Classes (SOCs) and preferred terms (PTs) according to the version of the MedDRA coding dictionary used for the study at the time of database lock. The actual version of the MedDRA coding dictionary used will be noted in the AE tables and in the clinical study report. Specific adverse events will be counted once for each subject for calculating percentages, unless stated otherwise. In addition, if the same adverse event occurs multiple times within a subject, the highest severity and level of relationship to investigational product will be reported.

9.2.1 Treatment-Emergent Adverse Events

Treatment-emergent AEs are defined as any AE with the onset that is after the first dose of study drug until 30 days after the last dose of the study drug. Events where the onset date is the same as the study drug start date are assumed to be treatment-emergent. If an incomplete or missing onset date was collected for an AE, the AE will be assumed to be treatment-emergent unless there is evidence to the contrary (e.g., the AE end date was prior to the date of the first dose of study drug). All treatment-emergent AEs will be summarized overall, as well as by primary MedDRA SOC and PT. The SOCs will be presented in alphabetical order, and the PTs will be presented in descending frequency order in the navitoclax + ruxolitinib group within each SOC.

The number and percentage of subjects experiencing treatment-emergent AEs will be summarized.

9.2.2 Adverse Event Overview

An overview of AEs will be presented consisting of the number and percentage of subjects experiencing at least one event for each of the following AE categories:

- Any treatment-emergent AE
- Any treatment-emergent AE with NCI toxicity Grade ≥ 3
- Any treatment-emergent AE with NCI toxicity Grade 3 or 4
- Any treatment-emergent AE with NCI toxicity Grade 3
- Any treatment-emergent AE with NCI toxicity Grade 4
- Any treatment-emergent AE with reasonable possibility related to navitoclax/placebo as assessed by the investigator
- Any treatment-emergent AE with reasonable possibility related to ruxolitinib as assessed by the investigator
- Any serious treatment-emergent AE
- Any treatment-emergent AE leading to discontinuation of navitoclax/placebo
- Any treatment-emergent AE leading to discontinuation of ruxolitinib

- Any treatment-emergent AE leading to interruption of navitoclax/placebo
- Any treatment-emergent AE leading to interruption of ruxolitinib
- Any treatment-emergent AE leading to dose reduction of navitoclax/placebo
- Any treatment-emergent AE leading to dose reduction of ruxolitinib
- Any treatment-emergent AE leading to death
- Any treatment-emergent AE related to COVID-19 infection
- All deaths
- Deaths occurring within 30 days after the last dose of study drug
- Deaths occurring more than 30 days after the last dose of study drug
- Deaths related to COVID-19 infection

9.2.3 Treatment-Emergent Adverse Events by SOC and/or PT

Treatment-emergent adverse event summaries will be presented by SOC and PT. Specific adverse events will be counted once for each subject for calculating percentages, unless stated otherwise. In addition, if the same adverse event occurs multiple times within a subject, the highest severity and level of relationship to investigational product will be reported.

In addition, treatment-emergent adverse events will be summarized by PT and sorted by decreasing frequency for the navitoclax + ruxolitinib arm, and summarized by SOC, PT and maximum NCI grade.

9.2.4 SAEs (Including Deaths) and Adverse Events Leading to Death

SAEs (including deaths) and AEs leading to death will be summarized by SOC and PT and in listing format.

9.2.5 Safety Topics of Interest

The safety topics of interest identified using standard MedDRA queries (SMQs) and custom searches are provided in [Appendix B](#).

The incidence of each safety topic of interest will be summarized by SOC and PT. The AEs overview described in Section 9.2.2 and a listing of subject data will be provided for each search.

In addition, for each search, the risk difference for the overall incidence and the corresponding 95% confidence interval (CI) will be computed and displayed in a forest plot and summary table. The risk difference will be defined as the incidence proportion of the navitoclax + ruxolitinib treatment arm minus the incidence proportion of the placebo + ruxolitinib treatment arm. The normal approximation to the binomial distribution will be used to compute the 95% CI.

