Life-Threatening	An event that, in the opinion of the investigator, would have resulted in immediate fatality if medical intervention had not been taken. This does not include an event that would have been fatal if it had occurred in a more severe form.
Hospitalization or Prolongation of Hospitalization	An event that results in an admission to the hospital for any length of time or prolongs the subject's hospital stay. This does not include an emergency room visit or admission to an outpatient facility.
Congenital Anomaly	An anomaly detected at or after birth, or any anomaly that results in fetal loss.
Persistent or Significant Disability/Incapacity	An event that results in a condition that substantially interferes with the activities of daily living of a study subject. Disability is not intended to include experiences of relatively minor medical significance such as headache, nausea, vomiting, diarrhea, influenza, and accidental trauma (e.g., sprained ankle).

Important Medical Event Requiring Medical or Surgical Intervention to Prevent Serious Outcome

An important medical event that may not be immediately life-threatening or result in death or hospitalization, but based on medical judgment may jeopardize the subject and may require medical or surgical intervention to prevent any of the outcomes listed above (i.e., death of subject, life threatening, hospitalization, prolongation of hospitalization, congenital anomaly, or persistent or significant disability/incapacity). Additionally, any elective or spontaneous abortion or stillbirth is considered an important medical event. Examples of such events include allergic bronchospasm requiring intensive treatment in an emergency room or at home, blood dyscrasias or convulsions that do not result in inpatient hospitalization, or the development of drug dependency or drug abuse.

All adverse events reported from the time of study drug administration until 30 days after the last dose/discontinuation of study drug administration will be collected, whether solicited or spontaneously reported by the subject. In addition, study procedure-related serious and nonserious adverse events will be collected from the time the subject signs the study-specific informed consent.

The following definitions will be used for serious adverse reactions (SARs) and suspected unexpected serious adverse reactions (SUSARs):

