6.0 Study Drug Duration and Compliance

For the safety analysis set, duration of treatment of navitoclax/placebo and ruxolitinib will be summarized for each treatment arm. Duration of treatment is defined for each subject as last dose date minus first dose date + 1. Duration of treatment will be summarized using the number of subjects treated, mean, standard deviation, median, minimum and maximum. In addition, the number and percentage of subjects in the following treatment duration intervals will be summarized:

- < 4 weeks (0 to 28 days),
- ≥ 4 weeks to < 12 weeks (28 to 84 days),
- ≥ 12 weeks to < 24 weeks (84 to 168 days),
- ≥ 24 weeks to < 36 weeks (168 to 252 days),
- ≥ 36 weeks to < 52 weeks (252 to 364 days),
- ≥ 52 weeks to < 78 weeks (364 to 546 days),
- ≥ 78 weeks to < 104 weeks (546 to 728 days),

- ≥ 104 weeks (≥ 728 days).

Subject-years of exposure of navitoclax/placebo and ruxolitinib will be summarized as duration of treatment from all subjects (days) divided by 365.25 for each treatment arm.

The relative dose intensity (RDI) will be summarized for navitoclax/placebo and ruxolitinib for each treatment arm. The RDI is defined as the ratio of the observed dose intensity (ODI) to the planned dose intensity (PDI) and expressed in a percentage. The ODI is defined as:

$$\text{ODI} = \frac{\text{Actual total dose}}{\text{Actual total duration of treatment exposure (days)}}$$

The PDI is defined as

$$\text{PDI} = \frac{\text{Planned total dose over actual duration of treatment}}{\text{Actual total duration of treatment exposure (days)}}$$

The actual total duration of treatment exposure in the above equations is defined as last dose date minus first dose date + 1 for navitoclax/placebo and ruxolitinib, respectively. The RDI will be summarized using the number of subjects treated, mean, standard deviation, median, quartiles, minimum and maximum.

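### Safety topics are compared between arms only by crude incidence, with no allowance for unequal time at risk

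*SAP*

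**What the plan says.** - **Measure.** SAP 9.2.5, for every topic: "the risk difference for the overall incidence and the corresponding 95% confidence interval (CI) will be computed and displayed in a forest plot". On what that difference is, the section says: "The risk difference will be defined as the incidence proportion of the navitoclax + ruxolitinib treatment arm", less that of the placebo arm. On the interval, it says: "The normal approximation to the binomial distribution will be used to compute the 95% CI". There is no person-time term.
- **Counting.** SAP 9.2: "Specific adverse events will be counted once for each subject for calculating percentages, unless stated otherwise".
- **Window.** SAP 9.2.1 counts these events as treatment-emergent: "any AE with the onset that is after the first dose of study drug until 30 days after the last dose of the study drug". SAP 4.0 defines study drug as any component of the assigned combination.
- **Collection.** Protocol 6.1: "All adverse events reported from the time of study drug administration until 30 days after the last dose/discontinuation of study drug administration" are collected. Events after that point cannot be recovered later.
- **Duration.** Protocol 4.1 sets no fixed treatment period. SAP 9.1 cuts safety data by calendar date, and SAP 8.1 places the primary analysis once ongoing subjects have 24 weeks of follow-up.
- **Exposure.** SAP 6.0: "Subject-years of exposure of navitoclax/placebo and ruxolitinib will be summarized as duration of treatment from all subjects (days) divided by 365.25" by arm. No adverse event analysis in SAP 9.1 to 9.5 uses person-time, time to first event or a fixed common period. The SAP's only event rate over person-time is for red cell transfusions (SAP 8.5.2).

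**The concern.** The time in which a subject can contribute an event depends on how long that subject stays on treatment. With the same underlying event rate, the arm with the longer windows shows the higher crude incidence. The risk difference in the forest plot therefore mixes the effect of navitoclax on event rates with any effect on time on treatment. It is the only between-arm adverse event estimate with a confidence interval in the plan, so it will be read as the added risk of navitoclax.

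The documents give reasons for an imbalance in either direction. Protocol 2.2 names thrombocytopenia as the main dose-limiting toxicity, which could shorten treatment in Arm A. The clinical hypothesis in Protocol 2.1 expects more durable responses, which could lengthen it. Neither document says which would dominate.

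**Working it through.** The documents state no adverse event rate, expected exposure or safety precision, so there is no figure to reproduce. The check is an illustration.

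**Inputs from the documents:** 230 subjects randomized 1:1, so about 115 per arm (Protocol 7.7); 30-day tail, τ = 30/365.25 = 0.0821 years (SAP 9.2.1).

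**Assumed inputs:** exponential time on all study drug with mean m = 1.0 year (Arm A) and 1.5 years (Arm B); constant event rate h of 0.30 or 0.45 per subject-year; a common maximum follow-up C of 1, 2 or 3 years, standing in for the calendar cutoff.

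**Formula.** With window W = min(time on drug + τ, C), crude incidence is 1 - E[exp(-hW)]:

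P = 1 - { e^(-hτ) × (1/m)/(h + 1/m) × [1 - e^(-(h + 1/m)(C - τ))] + e^(-(C - τ)/m) × e^(-hC) }

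**Worked case, C = 2:**
- Arm A, h = 0.30: 1 - (0.9757 × 0.7692 × 0.9174 + 0.1469 × 0.5488) = 23.1%
- Arm B, h = 0.30: 1 - (0.9757 × 0.6897 × 0.8434 + 0.2784 × 0.5488) = 28.0%
- Arm A, h = 0.45: 1 - (0.9637 × 0.6897 × 0.9380 + 0.1469 × 0.4066) = 31.7%

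Equal rates give 23.1 - 28.0 = -4.9 points. Rates of 45 v 30 give 31.7 - 28.0 = +3.7. The SAP's half-width for equal rates is 1.96 × √[(0.231 × 0.769 + 0.280 × 0.720)/115] = 11.3 points.

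| C (years) | Equal rates, 30 v 30: A v B, difference (half-width) | 45 v 30: A v B, difference (half-width) | 45 v 30, all at risk for full C |
|---|---|---|---|
| 1 | 18.1% v 20.2%, -2.1 (±10.2) | 25.6% v 20.2%, +5.4 (±10.8) | +10.3 |
| 2 | 23.1% v 28.0%, -4.9 (±11.3) | 31.7% v 28.0%, +3.7 (±11.8) | +14.2 |
| 3 | 24.4% v 30.9%, -6.5 (±11.5) | 33.1% v 30.9%, +2.2 (±12.1) | +14.7 |

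The last column is e^(-0.30C) - e^(-0.45C). A milder comparator gives both arms the same exponential time on drug (mean 1.0 or 1.5 years). The 45 v 30 difference is then +7.5 to +8.3 at C = 1, +8.6 to +9.9 at C = 2 and +8.7 to +10.1 at C = 3. The crude figures lie below either comparator.

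**Opposite imbalance** (Arm A 1.5, Arm B 1.0 years): equal rates give +2.1, +4.9 and +6.5 points.

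**Front-loaded event** (assumed 3 per year for the first 0.25 year, then 0.1 per year; fixed windows of 0.5 v 1.0 year): 1 - e^(-0.775) = 53.9% v 1 - e^(-0.825) = 56.2%, a difference of -2.2 points despite a twofold difference in window.

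**The case against.** **The crude difference is a legitimate quantity.** It describes the share of subjects on each regimen who had the event while under observation, and no test or alpha depends on it. That stands. It does not, however, separate event rate from time at risk, and nothing else planned for adverse events does.

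**Other outputs help.** Duration bands and subject-years (SAP 6.0) would reveal an imbalance. Laboratory summaries at scheduled visits (SAP 9.3) give a common-time view of platelets, neutrophils and liver tests. Overall survival compares deaths by time-to-event methods. This also stands, but none of it adjusts the adverse event comparison, and haemorrhage and serious infection have no laboratory counterpart.

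**The bias may be small.** It lies within the planned interval in every row of the table. Because study drug means any component, stopping navitoclax/placebo while ruxolitinib continues does not close the window, so the imbalance may be smaller than that in navitoclax exposure. Protocol 4.2 says the platelet effect may lessen with continued dosing, so thrombocytopenia may be front-loaded and little affected. All of this stands and limits the point.

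**Stronger readings that the documents do not support.** A reader might infer that a 50% higher rate could vanish entirely, or that equal rates could show an 8-point benefit. Under the assumed means, the formula h/(h + 1/m) gives exactly that: 0.45/1.45 = 0.30/0.967 = 31%, and 0.30/1.30 = 23% v 31%. But it ignores the data cutoff and the 30-day tail, both of which the SAP applies. A reader might also infer that navitoclax risk will be understated, or that serious infection, bleeding and liver injury are late events. The documents give neither an expected exposure difference nor the timing of these events.

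**Conclusion.** The point holds as a gap in the supplementary safety analysis. If total time on study drug differs between arms, the planned risk difference is biased toward showing more harm in the arm treated longer. Under the stated assumptions the bias is about 2 to 6.5 points when the true rates are equal. A 50% higher rate is reduced to about +5 to +2 points, against +10 to +15 with full equal windows or about +7.5 to +10 with equal exponential exposure. These sizes rest on assumed rates, durations and follow-up, a constant hazard, and stopping unrelated to event risk. With equal time on treatment there is no such bias. The primary efficacy test, alpha and sample size are unaffected. This is a cheap improvement, best specified before the exposure data by arm are seen.

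**What to change.** Keep the crude risk difference. For each Appendix B topic, and for serious and Grade ≥ 3 treatment-emergent events, show beside it:

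1. **First events per 100 subject-years at risk**, with the rate difference and 95% CI. Time at risk runs from first dose of any component to the earliest of first event, last dose of any component + 30 days, death or data cutoff. The subject-years in SAP 6.0 cannot be the denominator: they are per drug, omit the 30-day tail and do not stop at the first event.
2. **Cumulative incidence by arm at Week 24**, and at a later common time such as Week 48 when follow-up allows. Treat death, and closure of the window after permanent discontinuation of all study drug, as competing events; censor only at data cutoff or loss to follow-up. With death as the only competing event, stopping for toxicity would be handled as uninformative censoring.

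The two should be read together. The rate describes risk while under observation but assumes a roughly constant hazard. The cumulative incidence needs no such assumption and refers to a common time, but still reflects how many subjects stopped.

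Cost: a few extra tables and one new time-at-risk derivation from dates already collected.

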Clinical studies conducted to date have assessed safety, pharmacokinetics, and initial efficacy of navitoclax as a single agent and as combination therapy in subjects with hematological malignancies and subjects with solid tumors. The monotherapy recommended Phase 2 dose (RPTD) has been determined as 250 mg in chronic lymphocytic leukemia (CLL) (with a 100 mg lead-in period prior to Cycle 1) and 325 mg under the continuous dosing schedule in small cell lung cancer and other lymphoid malignancies (excluding CLL; with a 150 mg lead-in period prior to Cycle 1), although the starting dose was reduced to 250 mg in lymphoid malignancies as this was found to be more tolerable.⁵⁻⁸

Preclinical data suggest that navitoclax may overcome JAK2 resistance, resensitizing cells to JAK2 inhibition from ruxolitinib, and therefore may provide disease-modifying therapy in subjects with primary myelofibrosis (PMF) and secondary myelofibrosis (SMF).⁶ The combination of navitoclax and ruxolitinib in subjects with MF (Study M16-109) has demonstrated efficacy in subjects with persistent splenomegaly while receiving treatment with ruxolitinib for at least 12 weeks (AbbVie data on file). The median duration of prior ruxolitinib exposure before initiating navitoclax on Study M16-109 was 21 months (range 4 to 71 months). After 24 weeks of treatment with navitoclax and ruxolitinib, 30% of subjects achieved spleen volume reduction ≥ 35% (SVR₃₅). Additionally, spleen responses seem to deepen beyond 24 weeks of treatment, and the best overall SVR₃₅ was further improved to 43%. Symptom improvements were reported in 65% of subjects with 35% of subjects achieving ≥ 50%

reduction from baseline in total symptom score at Week 24. Additionally, reductions in bone marrow fibrosis of ≥ 1 grade were observed in 27% of subjects, suggesting this drug combination may be disease modifying. The safety profile was acceptable with the most common Grade ≥ 3 treatment-emergent AEs reported as thrombocytopenia and anemia. There were no serious adverse events of bleeding. There was 1 treatment-emergent death due to pneumonia that was assessed by the investigator as having no reasonable possibility of relationship to navitoclax.

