7.7 Sample Size Determination

Approximately 230 subjects will be enrolled using a 1:1 randomization ratio to Arm A and Arm B by the stratification factors (DIPSS+: intermediate-2 versus high risk, and platelet count: $\leq 200 \times 10^9/L$ versus $> 200 \times 10^9/L$). The null hypothesis H_0 will be tested against the alternative hypothesis H_1 using the stratified CMH test with two-sided significance level 0.05.

Based on published results, the SVR_{35W24} rate in the control arm (Arm B) is expected to be approximately 40%.¹⁵ True improvement in SVR_{35W24} from 40% to [REDACTED] is considered clinically meaningful.

This study with 230 subjects will have approximately 90% power if the true SVR_{35W24} rates in the control (placebo + ruxolitinib) and treatment (navitoclax + ruxolitinib) arms are 40% and [REDACTED], respectively.

With a total of 230 subjects, the study will also have approximately [REDACTED] power to detect a statistically significant OS improvement in the navitoclax + ruxolitinib treatment arm, assuming a true hazard ratio of [REDACTED]. A total of two OS analyses are planned: the first will be performed at the time of approximately 70% OS information (or [REDACTED] death events); the final OS Analysis will be performed when a total of [REDACTED] death events (100% OS information) have been observed. The Lan-DeMets alpha-spending function with O'Brien-Fleming boundary will be used to determine the efficacy boundaries for these planned OS analyses.

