4.0 Analysis Populations

The following population sets will be used for the analyses.

The Intent-to-Treat (ITT) Population includes all randomized subjects. Unless otherwise specified, the ITT Population will be used for all efficacy analyses. Subjects will be included in the analysis according to the treatment arms that they are randomized to.

The TSS Sensitivity Analysis Population includes all randomized subjects who meet the following criteria:

- subjects with baseline TSS score ≥ 12 ; or
- subjects with at least 2 symptoms with a baseline symptom score ≥ 3 .

The Safety Analysis Set consists of all subjects who received at least 1 dose of any component of the study drug. Subjects will be included in the analysis according to the study drug that they actually received.

The pharmacokinetic (PK) analysis population consists of all subjects who received at least 1 dose of navitoclax. The PK analysis population will be used for all PK analyses.

The study drug is defined as any component of navitoclax + ruxolitinib for subjects in Arm A and any component of placebo + ruxolitinib for subjects in Arm B.

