Appendix B. Definition of Safety Topics of interest

Safety topics of interest will be identified using the following search criteria:

Safety Topics of Interest	Criteria for Identification of Events
Thrombocytopenia	PTs: 10043554 Thrombocytopenia 10035528 Platelet Count Decreased
Neutropenia	PTs: 10016288 Febrile Neutropenia 10029354 Neutropenia 10029366 Neutrophil Count Decreased
Hemorrhagic Events	SMQ: 20000038 Haemorrhages (Narrow)
Serious Hemorrhagic Events Concurrent ^a with Grade 3 or 4 Thrombocytopenia	SAEs in the Hemorrhagic Events search concurrent with Grade 3 or 4 AE in Thrombocytopenia search
Serious Infections	SAEs in the SOC of Infections and Infestations
Serious Infections with Concurrent ^a with Grade 3 or 4 Neutropenia	SAEs in the Serious Infections search concurrent with Grade 3 or 4 AE in Neutropenia search
Drug-Induced Liver Injury (DILI) ^b	SMQs: 20000006 Drug Related Hepatic Disorders - Comprehensive (Broad) 20000007 Drug Related Hepatic Disorders - Severe Events Only (Narrow)

- a. An AE will be considered concurrent with cytopenia event if the onset date is no more than 7 days prior to the onset of the cytopenia and no more than 7 days after the end of the cytopenia event.
- b. The Drug Related Hepatic Disorders – Comprehensive SMQ (20000006) includes all PTs in the Drug Related Hepatic Disorders - Severe Events Only SMQ (20000007). Summaries will be provided for each SMQ.

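### The normal-approximation intervals for safety-topic risk differences have zero width at 0 vs 0 and upper limits that are too low for rare events

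*SAP*

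**What the plan says.** SAP 9.2.5 applies one rule to all safety topics: "for each search, the risk difference for the overall incidence and the corresponding 95% confidence interval (CI) will be computed". The results go into a forest plot and a summary table. The difference is navitoclax + ruxolitinib minus placebo + ruxolitinib, and the method is fixed in one sentence: "The normal approximation to the binomial distribution will be used to compute the 95% CI". The section sets no minimum event count and gives no alternative for zero or sparse cells.

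The topics are listed in SAP Appendix B. Some are broad, such as thrombocytopenia and neutropenia. Others are narrow intersections: "SAEs in the Hemorrhagic Events search concurrent with Grade 3 or 4 AE in Thrombocytopenia search" and "SAEs in the Serious Infections search concurrent with Grade 3 or 4 AE in Neutropenia search". A severe-events-only hepatic query is summarised separately as well.

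The denominator is set in SAP 4.0: "The Safety Analysis Set consists of all subjects who received at least 1 dose of any component of the study drug". The planned size is in Protocol 7.7: "Approximately 230 subjects will be enrolled using a 1:1 randomization ratio".

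**The concern.** The normal-approximation interval takes its width from the observed proportions alone. When an observed proportion is zero or close to it, the estimated variance is zero or close to it, and the interval shrinks just when the data are least informative.

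Very low counts are plausible here. For the Phase 2 combination study, Protocol 2.1 reports: "There were no serious adverse events of bleeding". That study enrolled a different, ruxolitinib-pretreated population, so it suggests rarity but does not supply a rate for this trial.

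What is at stake is how readers see the uncertainty. Protocol 2.2 identifies thrombocytopenia as the toxicity that has chiefly limited navitoclax dosing, so serious bleeding with severe thrombocytopenia is a row that readers will look for. If its upper limit is too low, the display suggests that an excess has been ruled out when it has not.

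**Working it through.** **Inputs**
- Method: normal approximation, 95%, two-sided (SAP 9.2.5). The SAP prints no formula. I read it as the usual Wald interval with unpooled variance and no continuity correction.
- Arm size: 230 / 2 = 115 (Protocol 7.7). This assumes that all subjects are treated as randomised, because the size of the safety set is not given.
- Event rates: not in the documents. All rates below are assumptions, shown over a range.
- The plan states no figure for this analysis, so there is none to reproduce.

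**Step 1. Intervals at given counts.** With d = p1 - p2, the Wald interval is d ± 1.96 × √[p1(1-p1)/115 + p2(1-p2)/115].
- 0 vs 0: both variance terms are 0, so the interval is 0 ± 0.
- 1 vs 0: p1 = 1/115 = 0.870%. The standard error is √(0.00870 × 0.99130 / 115) = 0.866%. The interval is 0.870 ± 1.697, or -0.83 to 2.57 points.

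The Miettinen-Nurminen (MN) interval contains every difference δ for which |d - δ| divided by its standard error is at most 1.96. That standard error comes from the maximum-likelihood rates constrained to differ by δ, with the variance multiplied by 230/229. Newcombe's hybrid-score interval is shown for comparison. All limits are in percentage points.

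| Events | Wald | MN | Newcombe |
|---|---|---|---|
| 0 vs 0 | 0.00 to 0.00 | -3.25 to 3.25 | -3.23 to 3.23 |
| 1 vs 0 | -0.83 to 2.57 | -2.39 to 4.78 | -2.44 to 4.76 |
| 2 vs 0 | -0.65 to 4.13 | -1.54 to 6.13 | -1.73 to 6.12 |
| 4 vs 0 | 0.13 to 6.83 | 0.18 to 8.62 | -0.39 to 8.60 |
| 10 vs 3 | 0.17 to 12.00 | 0.12 to 13.02 | -0.09 to 12.88 |

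**Step 2. How often 0 vs 0 arises.** With the same true rate p in both arms, the chance is (1-p)^230: 56% at 0.25%, 32% at 0.5%, 9.9% at 1% and 1.0% at 2%.

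**Step 3. Coverage.** For each pair of true rates, I summed the product of the two Binomial(115) probabilities over all outcomes whose interval contains the true difference. Misses are split by direction; the nominal figure is 2.5% per side.

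| True rates | Wald coverage | Upper limit too low | Lower limit too high | MN coverage |
|---|---|---|---|---|
| 1% vs 0.2% | 74.2% | 25.7% | 0.1% | 99.5% |
| 1.5% vs 0.2% | 82.3% | 17.6% | 0.1% | 99.3% |
| 2% vs 1% | 89.1% | 9.9% | 1.0% | 96.1% |
| 5% vs 1% | 93.2% | 5.6% | 1.1% | 93.6% |
| 10% vs 2% | 94.6% | 3.9% | 1.5% | 94.7% |

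At the lowest rates the two faults are largely the same one. At 1% vs 0.2% the chance of 0 vs 0 is (0.99 × 0.998)^115 = 25.0%, which accounts for nearly all of the 25.7%. At 2% vs 1% it is (0.98 × 0.99)^115 = 3.1% of the 9.9%, so most misses there come from short intervals at small non-zero counts.

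**Step 4. Behaviour with no true difference.** With equal rates, the Wald interval excludes zero with probability 1.8% at a rate of 1%, 4.3% at 2%, 4.4% at 3% and 4.7% at 5%. The maximum over all rates is 5.6%, near a rate of 50%, and Newcombe has the same maximum.

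**Step 5. Common topics.** At 80% vs 50%, Wald coverage is 94.8%. For 92 vs 58 events, Wald gives 17.9 to 41.3 points and MN gives 17.5 to 40.9.

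**The case against.** The strongest reply is that these intervals are descriptive. SAP 9.2.5 attaches no test, threshold or decision rule to them, and they lie outside the error control of SAP 12.0. For each search the same section also requires incidences, an adverse-event overview and a subject listing. SAP 9.2.4 adds serious and fatal events, and SAP 9.3 adds liver-threshold tables and plots. A reader of a 0 vs 0 row would see the zeros. All of this stands, and it is why the point is minor. It does not rescue the interval, whose only purpose is to show uncertainty.

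The second reply is that the poor coverage depends on chosen rates: 0.2% in the control arm means 0.23 expected events. That is fair. The documents give no topic rates, and by 5% vs 1% Wald is within two points of nominal. For common topics it is adequate.

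A reader might go further and infer that the Wald interval produces false safety signals by wrongly excluding zero. The calculations do not support this. With equal rare rates it excludes zero less than 5% of the time (Step 4). At 4 vs 0 it does exclude zero, but so does Miettinen-Nurminen, by a slightly wider margin (+0.18 against +0.13). In the scenarios with poor coverage a true difference exists, so excluding zero there is not an error.

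**Conclusion.** The rule as written gives wrong error bars for rare safety topics. The interval has no width at 0 vs 0. With small unequal rates it covers about 74% to 93% instead of 95%, and the error is mainly on the upper side. At 1 vs 0 events the upper limit is 2.6 points where the score interval gives 4.8. At 4 vs 0 it is 6.8 against 8.6. The excess risk that the data leave open is therefore understated.

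This rests on 115 treated subjects per arm, on reading the normal approximation as the plain Wald interval, and on assumed event rates. The zero-width result depends on none of the assumed rates or the arm size. Severity is minor, because the display is descriptive and only rare topics are affected.

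**What to change.** In SAP 9.2.5, replace the normal approximation with the Miettinen-Nurminen score interval for all safety topics. Name one method only, because score-type methods can disagree about zero at borderline counts (4 vs 0 and 10 vs 3 in Step 1). A single method for every topic avoids a count-based switching rule, and intervals for common topics barely change.

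Carrying over the exact unconditional limits that SAP 8.6 uses for efficacy subgroups would need care. Based on the raw difference they give ±13.3 points at 0 vs 0; based on the score statistic they give ±3.3.

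The cost is one SAP sentence, one code option and wider intervals for rare topics. The replacement is not perfect: at 5% vs 1% its total coverage (93.6%) is close to Wald's. Its upper limit is too low there in 2.0% of cases rather than 5.6%, while its lower limit is too high in 4.4% rather than 1.1%.
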